9.2.2.3 Reporting Serious Adverse Events After the Protocol-required Reporting Period

There is no requirement to monitor study subjects for new serious adverse events following the protocol-required reporting period after the end of study. However, these serious adverse events can be reported to Amgen. In some countries (eg, European Union [EU] member states), investigators are required to report serious adverse events

that they become aware of after the protocol-required reporting period after the end of study. If serious adverse events are reported, the investigator is to report them to Amgen within 24 hours following the investigator's knowledge of the event.

Serious adverse events reported outside of the protocol-required reporting period will be captured within the safety database as clinical trial cases for the purposes of expedited reporting.

9.3 Pregnancy and Lactation Reporting

If a pregnancy occurs in a female subject, or female partner of a male subject, while the subject is taking protocol-required therapies report the pregnancy to Amgen as specified below.

In addition to reporting any pregnancies occurring during the study, investigators should monitor for pregnancies that occur after the last dose of protocol-required therapies through 7 months after the last dose of AMG 820 or 4 months after the last dose of pembrolizumab.

The pregnancy should be reported to Amgen's Global Safety within 24 hours of the investigator's knowledge of the event of a pregnancy. Report a pregnancy on the Pregnancy Notification Worksheet ([Appendix C](#)). Amgen's Global Safety will seek to follow with the Investigator regarding additional information that may be requested.

If a female subject becomes pregnant during the study, the Investigator should attempt to obtain information regarding the birth outcome and health of the infant.

If the outcome of the pregnancy meets a criterion for immediate classification as a Serious Adverse Event (eg, female subject experiences a spontaneous abortion, stillbirth, or neonatal death or there is a fetal or neonatal congenital anomaly) the Investigator will report the event as a Serious Adverse Event.

If a female breastfeeds while taking protocol-required therapies report the lactation case to Amgen as specified below.

Any lactation case should be reported to Amgen's Global Safety within 24 hours of the investigator's knowledge of event. Report a lactation case on the Lactation Notification Worksheet ([Appendix C](#)). Amgen Global Patient Safety will follow-up with the Investigator regarding additional information that may be requested.

If a male subject's female partner becomes pregnant, the Investigator should discuss obtaining information regarding the birth outcome and health of the infant from the pregnant partner.

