- 217 Men of reproductive potential and women of childbearing potential who are unwilling to practice a highly effective method(s) of birth control while on study through 4 months after receiving the last dose of study drug. Highly effective methods of birth control are defined as those which result in a low failure rate (ie, less than 1% per year) when used consistently and correctly such as implants, injectables, combined oral contraceptives, intrauterine devices (IUDs), sexual abstinence or vasectomised partner.
- Note: Men and women who do not meet the definitions below are considered to be of reproductive potential or childbearing potential respectively.
- Men of non-reproductive potential are defined as having azoospermia, whether due to having had a vasectomy or due to an underlying medical condition.
 - Women not of childbearing potential are defined as: Any female who is postmenopausal defined as at least 12 months with no menses without an alternative medical cause; in women < 45 years of age, a high follicle stimulation hormone [FSH] level in the postmenopausal range may be used to confirm a postmenopausal state in women not using hormonal contraception or hormonal replacement therapy; in the absence of 12 months of amenorrhea, a single FSH measurement is sufficient OR have had a hysterectomy and/or bilateral oophorectomy, or bilateral salpingectomy at least 6 weeks prior to screening, OR has a congenital or acquired condition that prevents childbearing.
- 218 Women who are lactating /breastfeeding or who plan to breastfeed while on study through 4 months after receiving the last dose of study drug.
- 219 Women with a positive pregnancy test.
- 220 Women planning to become pregnant while on study through 4 months after receiving the last dose of study drug.
- 221 Subject has known sensitivity to any of the products or components to be administered during dosing.

- 222 Subject likely to not be available to complete all protocol-required study visits or procedures, and/or to comply with all required study procedures to the best of the subject and investigator's knowledge.
- 223 History or evidence of psychiatric, substance abuse, or any other clinically significant disorder, condition or disease (with the exception of those outlined above) that, in the opinion of the investigator or sponsor physician, if consulted, would pose a risk to subject safety or interfere with the study evaluation, procedures or completion.

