6.2.4.10.2 Contraception Requirements for AMG 820 and/or Pembrolizumab

AMG 820 and/or Pembrolizumab may have adverse effects on a fetus *in utero*.

Furthermore, it is not known if AMG 820 or pembrolizumab has transient adverse effects on the composition of sperm. Non-pregnant, non-breast-feeding women may be enrolled if they are willing to use acceptable method(s) of effective contraception or are considered of non-childbearing potential. Refer to [Section 4.2](#), exclusion criteria 214, for contraception requirements and definition of women of non-childbearing potential for this study. Refer to the informed consent form for acceptable method(s) of effective contraception for subjects to use in this study. Additional country-specific contraception requirements may be defined in a country-specific protocol supplement at the end of the Appendix Section of protocol as required by local laws and regulations.

Subjects should be informed that taking AMG 820 and/or pembrolizumab may involve unknown risks to the fetus (unborn baby) if pregnancy were to occur during the treatment and for 4 months after end of pembrolizumab. In order to participate in the study they must adhere to the contraception requirements described above for the duration of the study treatment and during the follow-up period defined in [Section 9.3](#) (Pregnancy and Lactation Reporting). If there are any concerns that a subject will not reliably comply with the requirements for contraception, that subject should not be enrolled into the study.

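### The protocol can be read as setting two different post-treatment contraception periods, 3 months apart when both drugs stop on the same day

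*Protocol*

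**What the plan says.** Four places in the current protocol text bear on how long contraception lasts after treatment.

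- **Section 4.2, criterion 217** turns away men and women of reproductive potential on this ground: "unwilling to practice a highly effective method(s) of birth control while on study through 4 months after receiving the last dose of study drug". **Criterion 220** uses the same period: "Women planning to become pregnant while on study through 4 months after receiving the last dose of study drug". Neither distinguishes AMG 820 from pembrolizumab.
- **Section 6.2.4.10.2, information on fetal risk.** Subjects are to be told of unknown risks to the fetus "if pregnancy were to occur during the treatment and for 4 months after end of pembrolizumab". The sentence concerns either drug, but the post-treatment period is counted from pembrolizumab alone.
- **Section 6.2.4.10.2, condition of participation.** The next sentence sets a condition for taking part: "they must adhere to the contraception requirements described above for the duration of the study treatment and during the follow-up period defined in". The place it then names is Section 9.3. The same section sends the reader to "exclusion criteria 214, for contraception requirements".
- **Section 9.3** asks investigators to monitor for pregnancies after the last dose "through 7 months after the last dose of AMG 820 or 4 months after the last dose of pembrolizumab". It gives no other post-treatment period.

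**The concern.** The entry criteria stop at 4 months, while a mandatory sentence elsewhere borrows a window that runs to 7 months after AMG 820. A site that follows the cross-reference and a site that works from the eligibility list can give subjects different instructions. The section that should settle the matter points to the wrong criterion.

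Section 6.2.4.10.2 itself says that either drug may harm a fetus, so the length of this period is a safety instruction. The ambiguity also makes it impossible to say whether a subject who stopped contraception after 4 months deviated from the protocol.

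**Working it through.** The plan gives no figure to reproduce. The check follows the cross-references and subtracts the stated periods.

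**Following the text**

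1. Criteria 217 and 220: 4 months after study drug.
2. Section 6.2.4.10.2, information sentence: 4 months after pembrolizumab, with no separate AMG 820 period.
3. Section 6.2.4.10.2, condition of participation: treatment plus the Section 9.3 follow-up period.
4. Section 9.3: 7 months after AMG 820 or 4 months after pembrolizumab. It does not say that the later date applies, although Sections 6.5 and 9.2.2.1 do say so for their windows.
5. Criterion 214 is HIV positivity. The contraception rule and the definition of non-childbearing potential are in criterion 217.

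**Size of the gap**

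Let *d* be the months for which pembrolizumab continues alone after the last AMG 820 dose. Section 6.2 has both drugs given on the same day, so *d* = 0 is the usual case. Section 6.2.1.3 allows one drug to continue without the other. Take study drug in criterion 217 to mean whichever drug is given last. In months after the last AMG 820 dose:

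- Criterion 217: 4 + *d*
- Section 9.3, if the later limb governs: max(7, 4 + *d*)
- Difference: max(0, 3 − *d*)

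| *d* | Criterion 217 | Section 9.3, later limb | Gap |
|---|---|---|---|
| 0 | 4 | 7 | 3 |
| 1 | 5 | 7 | 2 |
| 2 | 6 | 7 | 1 |
| 3 or more | 4 + *d* | 4 + *d* | 0 |

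If Section 9.3 is read through its pembrolizumab limb only, the period is 4 + *d* and the gap is 0 throughout. The possible difference is therefore 0 to 3 months, and 3 months when the last doses coincide and the AMG 820 limb counts.

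**Position relative to the safety visit**

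Assume 30.4 days per month and same-day last doses. Then 4 × 30.4 ≈ 122 days and 7 × 30.4 ≈ 213 days, so the disputed window is about 213 − 122 = 91 days. The safety follow-up visit, which includes a pregnancy test (Section 7.2.3), falls at 135 to 142 days. That leaves 213 − 142 = 71 to 213 − 135 = 78 days of the window after the visit. Long-term contacts (Section 7.2.4) are described as covering survival, disease status and subsequent therapy.

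**The case against.** The strongest reply is that Section 9.3 is a rule on monitoring and reporting pregnancies. It does not mention contraception, and monitoring may properly outlast a contraception duty. Section 6.2.4.10.2 also refers to requirements set out above it, which lead back to the 4-month text. This stands in part. It rules out the stronger reading, which a reader might infer, that the protocol requires contraception for 7 months: that duty arises only through a loose cross-reference to a window with an unresolved *or*. It does not remove the ambiguity, because Section 6.2.4.10.2 expressly ties contraception to a Section 9.3 period and Section 9.3 offers only this one.

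Other inferences also go too far:

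- **That following either passage breaches the other.** The shortfall runs one way. Contraception for 7 months satisfies a 4-month rule when the last doses coincide; only stopping at 4 months can fall short.
- **That every subject of reproductive potential is affected.** The gap closes once pembrolizumab has continued alone for 3 months.
- **That subjects are in fact given conflicting instructions.** The consent form and any country supplement are not available, so this cannot be checked. Nor do the documents give a half-life or reproductive-toxicity figure from which to judge exposure between months 4 and 7.
- **That the breastfeeding criterion (218) has the same conflict.** The Section 9.3 window covers pregnancies only; its lactation reporting concerns breastfeeding while on therapy.

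The wrong criterion number is clerical, and a reader can find 217 from its content. Amendment 2 records that the sponsor has decided to stop investigating the combination, which limits how many subjects a correction would reach. Treatment may still last up to 24 months (Section 3.5.1), and the disputed window comes after the last dose.

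**Conclusion.** This is an internal inconsistency in current text and should be corrected. The protocol supports two readings of the post-treatment contraception period. They differ by 3 months when the last doses coincide, and by less or nothing if pembrolizumab continues alone. A subject who stops contraception at 4 months meets criterion 217 but may breach the requirement that runs through Section 9.3.

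The conclusion rests on two assumptions: that the monitoring window is the period Section 6.2.4.10.2 means, since Section 9.3 has no other, and that the AMG 820 limb counts. It does not establish which period is right, or what subjects have been told.

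**What to change.** Reconcile criteria 217 and 220, Section 6.2.4.10.2 and Section 9.3, so that the contraception period after each drug is stated once and the other places refer to it. In doing so:

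- State how the two drug periods combine when the last doses differ.
- State whether the Section 9.3 window governs contraception or only pregnancy reporting. If only reporting, reword the sentence in Section 6.2.4.10.2 that relies on it.
- Bring the fetal-risk information in Section 6.2.4.10.2 into line, including what it says about AMG 820.
- Change the cross-reference in Section 6.2.4.10.2 from criterion 214 to 217.
- Check the consent wording against the result.

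The sponsor decides which period applies. The cost is amendment wording and, if the consent form differs, a consent update. Sample size and the statistical analyses are unaffected.

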9.4 Pembrolizumab Events of Clinical Interest

Selected adverse events known as Pembrolizumab Events of Clinical Interest must be reported to Amgen within 24 hours of the investigator's knowledge of the event regardless of attribution to pembrolizumab.

For the time period beginning at time of first dose of pembrolizumab through 135 (+7) days following cessation of pembrolizumab treatment, or 135 (+7) days after initiation of a new anti-cancer therapy, any Pembrolizumab Events of Clinical Interest, or follow-up to a Pembrolizumab Events of Clinical Interest, whether or not related to the pembrolizumab, must be reported within 24 hours to Amgen.

Pembrolizumab Events of Clinical Interest for this trial include:

- an overdose of pembrolizumab, as defined in Section 9.5
- potential drug-induced liver injury (DILI) from pembrolizumab as defined in [Section 9.6](#)

Subjects should be assessed for possible Pembrolizumab Events of Clinical Interest prior to each dose.

9.5 Definition of an Overdose of Pembrolizumab for This Protocol and Reporting of Pembrolizumab Overdose

For the purpose of this trial, an overdose of pembrolizumab will be defined as any dose of pembrolizumab equal to or greater than 300 mg. No specific information is available on the treatment of overdose of pembrolizumab. In the event of overdose, pembrolizumab should be discontinued and the subject should be observed closely for signs of toxicity. Appropriate treatment should be provided if clinically indicated.

If an adverse event(s) or serious adverse event(s) is associated with ("result from") the overdose of pembrolizumab, the adverse event(s) or serious adverse event is to be reported to Amgen as described in [Section 9.2.2](#). In addition, the adverse event(s) or serious adverse event(s) associated with ("result from") the overdose of pembrolizumab should be reported as Event of Clinical Interest as described in Section 9.4.

9.6 Definition and Reporting of Pembrolizumab Drug-induced Liver Injury

For the purpose of this trial, potential DILI associated with (“resulting from”) pembrolizumab will be defined as:

- elevated AST or ALT $\geq 3 \times$ ULN and elevated total bilirubin $\geq 2 \times$ ULN
- AND ALP $<$ than $2 \times$ ULN, as determined by way of protocol-specified laboratory testing or unscheduled laboratory testing.*

*Note: These criteria are based upon available regulatory guidance documents. The purpose of the criteria is to specify a threshold of abnormal hepatic tests that may require an additional evaluation for an underlying etiology. The trial site guidance for assessment and follow-up of these criteria will be provided in separate guidance document entitled, the pembrolizumab Event of Clinical Interest Guidance for Potential DILI in Clinical Trials.

To facilitate appropriate monitoring for signals of DILI associated with pembrolizumab, cases of concurrent DILI according to the criteria specified above require the following:

- The event is to be reported to Amgen as an adverse event of potential DILI within 24 hours of discovery or notification of the event (ie, before additional etiologic investigations have been concluded)
- The appropriate CRF (eg, Event CRF) that captures information necessary to facilitate the evaluation of treatment-emergent liver abnormalities is to be completed.
- Workup to confirm DILI should be immediately initiated as described in the pembrolizumab Event of Clinical Interest Guidance for Potential DILI in Clinical Trials document. Any confirmed event of DILI is to be reported as a serious adverse event within 24 hours after confirmation of the event.

Other events of hepatotoxicity and potential DILI are to be reported as serious adverse events if they meet the criteria for a serious adverse event defined in [Section 9.1.3](#).

10. STATISTICAL CONSIDERATIONS

10.1 Study Endpoints, Analysis Sets, and Covariates

10.1.1 Study Endpoints

10.1.1.1 Primary Endpoints

- Dose limiting toxicities (DLT), treatment-emergent adverse events, treatment-related adverse events and clinically significant changes in vital signs, physical examinations, and clinical laboratory tests
- Objective response rate (ORR) per irRECIST in subjects treated at the recommended combination dose

10.1.1.2 Secondary Endpoints

- OR per RECIST 1.1; TTR, DOR and TTP; OS and PFS at 6 and 12 months
- PK parameters for AMG 820 including, but not limited to, maximum observed concentration (C_{max}) and minimum observed concentration (C_{min}). In addition, area under the concentration-time curve (AUC) and, if feasible, half-life ($t_{1/2}$) for AMG 820.
- CD4, CD8 & CD68 cells number in fresh pre-treatment biopsies

10.1.1.3 Exploratory Endpoints

- Anti-AMG 820 and anti-pembrolizumab antibodies levels
- Biomarker readouts at baseline and treatment related changes
- PK parameters for pembrolizumab include, but are not limited to, concentration at end of pembrolizumab infusion administration, maximum observed concentration (C_{max}) and minimum observed concentration (C_{min}).

10.1.2 Analysis Sets

The analysis of all endpoints, unless noted otherwise, will be conducted on the Safety Analysis Set defined as all subjects that are enrolled and receive at least 1 dose of AMG 820. The analysis of DLT will be restricted to DLT-evaluable subjects (see [Section 6.2.1.2.2](#)). The PK Analysis Set will contain all subjects who have received at least 1 dose of the investigational product and have at least 1 PK sample collected. These subjects will be evaluated for PK analysis unless the number of data points required for analysis is not enough, or significant protocol deviations have affected the data, or if key dosing or sampling information is missing.

10.1.3 Covariates and Subgroups

The relationship of covariates to efficacy endpoints will be explored if appropriate. Biomarker data (eg, PD-L1 expression) may be incorporated in additional exploratory subgroup or multivariate analyses. The exploratory analyses of biomarkers may be performed after collection of all samples during the conduct of the study and therefore may be reported after the primary analysis of the safety and efficacy endpoints.

10.2 Sample Size Considerations

It is anticipated that 67 to 197 subjects will be enrolled overall in this study.

Part 1 will enroll 6 to 18 evaluable subjects. The sample size in Part 1 is based on practical consideration, and it is consistent with conventional oncology studies with the objective to evaluate the safety and tolerability of a treatment combination. With 6 subjects in a cohort, there is a 47-91% probability of observing at least one DLT if the true DLT rate is 10-33%.

Part 2 evaluation of efficacy will include at least 6 subjects from part 1 who have been treated with the recommended combination dose, and will enroll additional CRC, pancreatic cancer and NSCLC subjects up to maximum 185 subjects overall. The sample size in each group evaluated in Part 2 is chosen to test whether AM820 can enhance the anti-tumor activity observed historically with pembrolizumab alone and/or overcome lack of response to pembrolizumab monotherapy. For each group and sub-group enrollment may stop early due to insufficient clinical activity. The pre-planned recommendation for early termination is based on ORR (evaluated when the subjects complete at least 6 months of treatment or earlier if already reaching the recommended number of responders), nonetheless the DLRT (see [Section 6.2.1.2.1](#)) will make the decision for early termination after reviewing all available safety, efficacy, pharmacokinetic and pharmacodynamic data.

Group 1 will consist of up to 43 subjects with MMR-proficient CRC (only 18 enrolled initially in the first stage) who are naïve to anti-PD-1/PD-L1/CSF-1/CSF-1R treatment. In [2015, Le et al](#) reported a pembrolizumab objective response rate (ORR) per RECIST1.1 and irRC of 0% (0 of 18 patients) for MMR-proficient colorectal cancers. It is anticipated that the combination treatment of AMG 820 and pembrolizumab will have an ORR of 25% or higher in MMR-proficient CRC tumors; an ORR of 10% or less is considered to be insufficient anti-tumor activity to warrant future research. If 2 or fewer of the initial 18 subjects have an objective response then the recommendation is for enrollment to Group 1 be stopped for futility. If 8 or more of the 43 subjects have an objective response then the true ORR is determined to be >10%. This Simon Two-Stage design provides 80% power when the true ORR is 25% while maintaining a 1-sided, 5% alpha error when the true ORR is 10% or lower.

Group 2 will consist of up to 29 subjects with advanced pancreatic cancer (only 10 enrolled initially in the first stage) who have not received prior treatment with a PD-1/PD-L1/CSF-1/CSF-1R inhibitor. In [2012, Brahmer et al](#) reported a pembrolizumab ORR of 0% (0 of 14 patients) for pancreatic cancer. It is anticipated that the combination treatment of AMG 820 and pembrolizumab will have an ORR of 20% or higher in pancreatic tumors; an ORR of 5% or less is considered to be insufficient anti-tumor activity to warrant future research. If none of the initial 10 subjects have an objective response then the recommendation is for enrollment to Group 2 be stopped for futility. If 4 or more of the 29 subjects have an objective response then the true ORR is determined to be >5%. This Simon Two-Stage design provides 80% power when the

true ORR is 20% while maintaining a 1-sided, 5% alpha error when the true ORR is 5% or lower.

Group 3 will consist of up to 55 subjects (only 19 enrolled initially in the first stage) with NSCLC who have not received prior treatment with a PD-1/PD-L1/CSF-1/CSF-1R inhibitor, and who have tumor PD-L1 expression <50%. [Garon et al in 2015](#) reported a pembrolizumab ORR per RECIST1.1 of 13.1% (28 of 214 patients) for NSCLC patients with tumor PD-L1 expression <50%, and an ORR of 14.4% (21 of 146 patients) for those with tumor PD-L1 expression from 1% to 49%. It is anticipated that the combination treatment of AMG 820 and pembrolizumab will have an ORR of 30% or higher in low PD-L1 expressing subjects; an ORR of 15% or less is considered to be insufficient anti-tumor activity to warrant future research. If 3 or fewer of the initial 19 subjects have an objective response then enrollment to Group 3 will be stopped for futility. If 13 or more of the 55 subjects have an objective response then the true ORR is determined to be >15%. This Simon Two-Stage design provides 80% power when the true ORR is 30% while maintaining a 1-sided, 5% alpha error when the true ORR is 15% or lower.

Group 4 will consist of up to 58 NSCLC who received prior treatment with a PD-1/PD-L1 inhibitor, and failed to respond to or relapsed during therapy. These subjects must be also naive to anti-CSF-1/CSF-1R agents. There will be two sub-groups. Sub-group 4a will enroll up to 29 (only 10 enrolled initially in the first stage) subjects who have tumor PD-L1 expression <50% (see [Garon et al., 2015](#)) while sub-group 4b will enroll up to 29 subjects who have tumor PD-L1 expression \geq 50% (only 10 enrolled initially in the first stage). It is anticipated that the combination treatment of AMG 820 and pembrolizumab will have an ORR of 20% or higher in these NSCLC subjects; an ORR of 5% or less is considered to be insufficient anti-tumor activity to warrant future research. If none of the initial 10 subjects in a sub-group have an objective response then the recommendation is for enrollment to the sub-group be stopped for futility. If 4 or more of the 29 subjects in the sub-group have an objective response then the true ORR is determined to be >5%. This Simon Two-Stage design provides 80% power when the true ORR is 20% while maintaining a 1-sided, 5% alpha error when the true ORR is 5% or lower.

